- 1. **Intervention (Fitbit) arm.** The intervention arm will wear a Fitbit for a 16-week period (**Figure 2**). **General Principles of an aerobic activity regimen:**

As the principal muscles affected by PTS are the lower limb muscles, we have opted to use a walking-jogging program to capture steps/day by the Fitbit. This will target all potentially affected muscles (quadriceps, hamstrings and gastrocnemius/soleus). If preferred by the subject, other weight bearing exercises could replace the walk/jog, for example, dancing or team sports such as basketball or volleyball. Because of the unfamiliarity with activity trackers, subjects will be provided with hands-on training to promote successful use of the Fitbit and Fitabase.

a. Schedule and procedures (Table 1): After consent (baseline visit), subjects in this arm will receive a standardized 15-20 minute education session on PTS (what constitutes PTS, why patients get it, how to manage it) and enhanced activity after DVT. Subjects will be asked to wear the Fitbit for a period of four weeks to establish baseline or 'habitual' activity. Using steps/day data received at the end of four weeks, we will determine an individualized activity prescription of 'target steps/day', corresponding to a 25% increase above the baseline.

Table 1	Visit 1	Visit 2	Visit 3
	12 wks post DVT Dx (\pm 2 weeks)	16 wks after Visit 1 (\pm 4 weeks)	8 wks after Visit 2 (\pm 4 weeks)
	SOC Visit	SOC Visit	SOC Visit (Exit Visit)
ALL SUBJECTS			
Informed Consent	X*		
Full Medical History and Exam	X	X	
Biomarker Testing [^]	X\$	X	X
FXIII, D-dimer, CRP	X	X	X ^{^^}
QOL forms	X	X	X
PTS Assessment		X	X
ECS and Log	X	X~	X~
Activity Logs/ Questionnaire	X	X	X
Medication Log***	X	X	X

Phone Calls (monthly)	X	X	
Formal Education Session	X		
Honoraria**	X	X	X
SUBJECTS IN FITBIT ARM			
Hands on Fitbit Training	X		
Steps/Day Data (weekly)	X	X	X
Phone Calls (weekly)	X	X	
Return Fitbit			X

*Informed consent can occur any time after DVT diagnosis until Visit 1; ^Biomarker testing includes: D-Dimer, FVIII, Thrombin generation, markers of fibrinolysis; \$Biomarker testing at Visit 1 may be combined with other SOC labs for those still on anticoagulation at this time; ~ only ECS logs; ** \$25 at Visit 1 and 2, and \$50 at Visit 3; ***Medication logs only for participants on Rivaroxaban or Xarelto; ^^Factor VIII, D-dimer, and CRP can be completed as research procedures at Visit 3 for participant's whose values were within normal range at Visit 2.

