Subjects will be asked to maintain the target steps/day for a period of 8 weeks. At the end of this period, subjects will either maintain the increased activity or resume habitual activity for another 4 weeks, per patient preference. A phone call will be made periodically for encouragement and to ensure adherence to the activity regimen throughout the initial 16-week period. Subjects will have another visit 8 weeks (± 4 weeks) after the end of the 16-week period corresponding to the ~ 9 month post-diagnosis SOC visit. For subjects having difficulty with the activity prescription or use of the Fitbit, a phone call or face-to-face session will be arranged with the study research coordinator and physical therapist. Such changes will be carefully documented.

2. **Control arm.** The control intervention will consist of:
 - 1) a standardized 15-20 minute education session on PTS (what constitutes PTS, why patients get it, how to manage it) and benefits of enhanced activity

(activity will not be specifically addressed and will be up to the choice of the subject) after DVT; 2) monthly phone contacts will be made to check in with patients/families and remind them about completion of activity logs and follow-up visits.

Study assessments for both arms

1. Biomarker testing: Blood for biomarker of coagulation activation (D-dimer, FVIII, thrombin generation), markers of inflammation (CRP), and markers of fibrinolysis {modified thromboelastogram (TEG) with fibrinolysis, PAI-1, will be obtained at each visit One and a half extra teaspoons will be collected at each visit for a total of 4.5 teaspoons collected during the subject's time in the study.}
2. Elastic compression stockings (ECS)
 - i. Subjects in both arms will be provided with custom fitted compression stockings and their use will be tracked using ECS logs throughout study period. In general, SOC recommendations are to wear ECS starting after the diagnosis of DVT and to continue as long as they provide benefit in regards to pain and swelling, up to a period of two years post DVT diagnosis. For the sake of the study, their use will be documented strictly during the study period.
3. Activity log completion during the intervention period will be used to record physical activities. These logs will capture information on the type of activity, and the frequency and duration of activity

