4. Quality of life (all visits): QoL will be measured using the PedsQL™ which is a modular approach to measure generic health related quality of life in both healthy children and adolescents, as well as those with acute and chronic health conditions. It consists of structured interview with the parents and the child with 23 items divided among 4 sub-scales to assess function in 4 domains: Physical; Emotional; social; and School. The instrument is brief, takes 15

minutes to administer, and is developmentally adjusted for a broad age range.

5. PTS : Modified Villalta's scale and Marilyn-Manco Johnson Instruments, the two validated PTS scales, will be used to diagnose and grade severity of PTS at the 6 month mark corresponding to Visit 2 and the 9 month mark (corresponding to Visit 3). The principal and co-investigators will complete PTS evaluations as is standard of care at Visit 2 and Visit 3. In addition, a blinded PTS assessment will also be completed by the physical therapist (currently routinely assigned to the Thrombosis and Bleeding Disorders Program) at both visits.
6. Medication adherence: Anti-Xa and INR will be collected for participants on lovenox and warfarin, respectively. Families with participants on Rivaroxaban will be asked to complete a medication log because no assay will be used to measure adherence for Rivaroxaban. The medication log will measure compliance with anticoagulation during active treatment period and will include the subject's specific anticoagulant, dose, and date and time medication was taken.

See appendix for copies of above questionnaires, administration and scoring procedures.

IV. PARTICIPANT TIMELINE

All study visits will coincide with standard-of-care visits for patients with VTE at our center. All visits will be allowed a time window to accommodate preferences of subjects and families \pm 2 weeks for visit 1 and \pm 4 weeks for visit 2 and 3.

Study assessments: (Table 1 for schedule of events).

V. MODIFICATIONS

a. RISKS

- i. Blood Draws: Risks associated with drawing blood include minimal discomfort and/or bruising, infection,

- excess bleeding, clotting, and/or fainting are possible.
- ii. Doppler Ultrasound: There are no risks from the sound waves used for ultrasound. The test is not painful and does not have any radiation. This will be done as per standard of care.
- iii. Skin irritation or allergies with wearing the activity tracker
- iv. Injuries or falls related to increased physical activity

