Clinical information will be collected from each patient's electronic medical record at all visits while on study. This information will include the following: name, gender, race, ethnicity, date of birth, current medications, social history, patient medical and hospitalization history; family history, physical exam and laboratory results. Additional information to be collected from self reported diaries include adherence data and adverse reaction data. Returned diaries will be maintained in a research binder, while medical history, lab results, and medications will be recorded in the electronic medical record and then on electronic Case Report Forms (eCRF). Contact phone numbers for parents and relatives will be collected for the interim visit phone calls.

b. DATA MANAGEMENT

The eCRF will be housed in UT Southwestern REDCap. REDCap is a self-managed, secure, web-based data support system. The data is backed up offsite nightly and hosted in a secure environment maintained by Information Resources. This password protected study database will include a subject's personal identifiers and all Protected Health Information (PHI) such as medical history. All personnel who will be accessing the data will be trained in REDCap and have individual user ID and passwords. Subjects will have a study ID number that will be utilized in lieu of personally identifiable information for all research data provided to statisticians.

c. STATISTICAL ANALYSES

The following will be calculated: the proportion of screened patients who fully met trial eligibility criteria, the proportion of eligible patients who consented to participate, the proportion in the physical activity/ Fitbit group who adhered to prescribed activity, and the proportion of randomized patients who completed the trial (in total, and by allocated intervention). The feasibility outcomes will be reported descriptively

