Appendix 2 - Health-Related Quality of Life (QoL) Instruments

Appendix 3 – Medication Administration Log (For participants on Rivaroxaban)

Appendix 4 – Electronic Compression Stocking Log

Appendix 5 – Activity Log/questionnaire (*Initial and Follow Up*), *Godin questionnaire*

Appendix 1

A- Manco-Johnson Instrument (MJI)

PHYSICAL FINDINGS

Please measure to nearest tenth of one centimeter

Limb Circumference Measurements	Right	Left
Mid-proximal limb	_____ . _____ cm	_____ . _____ cm
Mid-distal limb	_____ . _____ cm	_____ . _____ cm

Basic CEAP Mark an "X" where applicable/present.

Physical Findings	Right	Left
0. No visible or palpable signs of venous disease		
1. Swelling, with or without pitting edema		
2. Dilated collateral circulation of extremity only		
3. Skin changes ascribed to venous disease (i.e., pigmentation, venous eczema)		
4. Skin changes as in 3 with ulceration or superior vena cava syndrome		

FUNCTIONAL FINDINGS (Pain Symptoms)

Wong-Baker Faces Pain Rating (Oucher Scale: Score 0-5 for each)

Pain Outcome: Wong-Baker (Oucher) Scale	Right	Left
With aerobic exercise only		
With activities of daily living		
At rest		

If pain is present (i.e., score 1-5): Does the pain interfere with activities?

YES NO

Comments:

Wong-Baker FACES Pain Rating Scale

Aerobic exercise only: Implies that symptoms are present only when child engages in vigorous age-appropriate sport such as running, lap swimming, soccer, basketball or volleyball.

Activities of daily living: Implies that a child is symptomatic when engaging in ordinary age-appropriate activities in the home, school and community short of organized sports and vigorous aerobic activities. These symptoms limit and alter a child's ordinary day-to-day activities such as walking at school, shopping with the family or participation in a birthday party.

At rest: Implies a constant presence of symptoms that is independent of activity. The child's daily life is severely limited by symptoms.

Signs	
Edema	1
Dilated superficial collateral veins	1
Venous stasis dermatitis	1
Venous stasis ulcers	1

Symptoms	
Chronic lower-extremity pain	
• Limiting aerobic activities	0-5
• Limiting activities of daily living	0-5
• At rest	0-5
Post Thrombotic Syndrome absent	0
Any Post-Thrombotic Syndrome present	≥ 1
Physically and functionally significant PTS	Signs ≥ 1 and Symptoms ≥ 1

B- Modified Villalta Score

Symptoms	
Pain or abnormal use	1
Swelling	1
Signs	

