Scoring Procedure	
Step 1: Transform Score Items are reversed scored and linearly transformed to a 0-100 scale as follows: 0=100, 1=75, 2=50, 3=25, 4=0
 
Step 2: Calculate Scores Score by Dimensions
 
 • If more than 50% of the items in the scale are missing, the scale scores should not be computed • Mean Score= Sum of the items over the number of items answered 
Psychological Health Summary Score= sum of the items over the number of items answered in the Emotional, Social, and School Functioning Scales.
 
Physical Health Summary Score= Physical Functioning Scale Score
 
Total Score: Sum of all the items over the number of items answered on all the scales.

Interpretation and Analysis of missing Data	If more than 50% of the items in the scale are missing, the Scale Scores should not be computed If 50% or more items are completed: impute the mean of the completed items in a scale

Appendix 3

DAILY MEDICATION ADMINISTRATION LOG

Name: Medication:

*nose bleeds, mouth bleeding, GI bleeding, heavy periods, bruising, burning and pain with shots, hair loss

Appendix 4

COMPRESSION STOCKINGS LOG

Name:

Compression Stocking type: Knee-high Thigh-high Arm sleeve

Compression level: 15-20 mm Hg 20-30 mm Hg 30-40 mm Hg

*Discomfort, worsening of pain, color changes, ulcers, difficulty wearing

Appendix 5

Physical Activity Questionnaire (Initial)

Start time: _____ End time: _____

This is short survey to find out about your level of physical activity before and after you developed a blood clot. These includes sports or dance that make you sweat or make your legs feel tired, or games that make you breathe hard, like tag, skipping, running, climbing, and others.

Your answers will help us understand how a blood clot affects your ability to be active. We believe your answers will help us treat you and other children with blood clots better.

Remember:

1. There are no right or wrong answers- this is not a test.
2. Please answer all questions as honestly and accurately as you can- this is very important.

ID : _____

Age: _____

Sex: M _____ F _____

Grade: _____

BEFORE the diagnosis of a blood clot:

Answer the following questions for the time before you had a blood clot.

1. Were you involved in any physical activity?

Yes No

2. If yes, was this physical activity part of:

- Recreation/leisure (sports/game/exercise)
- Work/School
- Transportation

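### The only form that lists bleeding and injection reactions goes to rivaroxaban subjects alone, so safety capture is uneven by anticoagulant and, through call frequency, by arm

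*Combined protocol and SAP*

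**What the plan says.** Section II.a (Data Collection Methods) lists what is taken from the medical record at visits and then states: "Additional information to be collected from self reported diaries include adherence data and adverse reaction data".

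Three diaries are described.

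- **Medication log (Appendix 3).** The Table 1 footnote reads "Medication logs only for participants on Rivaroxaban or Xarelto". Item 6 (Medication adherence) under Study assessments for both arms gives the reason: "Families with participants on Rivaroxaban will be asked to complete a medication log because no assay will be used to measure adherence for Rivaroxaban". The list of appendices also labels it a rivaroxaban form. For the other two drugs, item 6 states: "Anti-Xa and INR will be collected for participants on lovenox and warfarin, respectively". The Appendix 3 form carries an asterisked list: "nose bleeds, mouth bleeding, GI bleeding, heavy periods, bruising, burning and pain with shots, hair loss".
- **Activity log (all subjects).** Item 3 of the same section says: "These logs will capture information on the type of activity, and the frequency and duration of activity".
- **Compression stocking log (Appendix 4, all subjects).** Its list is "Discomfort, worsening of pain, color changes, ulcers, difficulty wearing".

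Anticoagulation can overlap with the activity period. A Table 1 footnote provides for subjects still being treated at Visit 1, and Concomitant Care item b keeps those on long-term prophylaxis eligible. The Fitbit arm aims for a 25% rise over baseline steps and may substitute team sports such as basketball. The Risks section names injuries and falls from greater activity.

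**The concern.** The medication log appears to do two jobs: it tracks adherence, and it lists reactions. The restriction to rivaroxaban is justified by the first job only. Anti-Xa and INR take over that job for Lovenox and warfarin, but neither records a nosebleed or a bruise. Restricting the form for an adherence reason therefore also removes the reaction list from subjects who may have the same events.

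The list itself shows the mismatch. It includes pain with injections, and of the three drugs named in item 6 only Lovenox is injected. That item cannot be recorded for the subjects to whom it applies.

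What is at stake is the safety description that a pilot should hand to the larger trial: how often bleeding occurs when children, some of them anticoagulated, are asked to do more. If the method of finding out differs by drug and by arm, that description is hard to read.

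**Working it through.** The plan gives no figure on this point, so the check sets the sections side by side.

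**Step 1. What each group has.**

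| Source | Rivaroxaban | Lovenox | Warfarin |
|---|---|---|---|
| Adherence measure (item 6) | Medication log | Anti-Xa | INR |
| Diary listing bleeding and bruising (Appendix 3) | Yes | None | None |
| Diary listing injection reactions (Appendix 3) | Yes, though the drug is not injected | None | None |
| Activity and stocking logs | Yes, no bleeding item described | Same | Same |
| Visits, medical record, calls, activity questionnaire | Yes | Yes | Yes |

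The rule on who receives the log is the same in all three places where it appears (Table 1 footnote, item 6, list of appendices), so it is not a slip in one line.

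**Step 2. What the remaining sources ask.**

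- Section III.a provides for a physical examination, including skin, at each visit. Table 1 marks the full history and examination at Visits 1 and 2 only.
- Section II.a takes hospitalization history, examination and laboratory results from the record.
- The activity questionnaires (Appendix 5) ask whether illness or anything else limited normal activity, with free text. They do not ask about bleeding.
- Calls in the Fitbit arm are for encouragement and adherence. Calls to controls are for checking in and for reminders about logs and visits. No bleeding question is specified for either.

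**Step 3. Contact frequency by arm.** Table 1 lists monthly calls for all subjects and weekly calls for the Fitbit arm. Over the 16-week period, counting a month as 4 weeks:

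- monthly: 16 / 4 = about 4 calls;
- weekly: 16 / 1 = 16 calls.

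The Fitbit arm thus has about 16 / 4 = 4 times as many occasions on which a bleed could be mentioned. This assumes that the weekly row of Table 1 is followed; the text for that arm says only that calls are periodic.

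**Step 4. How many subjects.** The number without a bleeding diary is

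44 × (share still anticoagulated after Visit 1) × (share of those not on rivaroxaban).

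The documents give neither share. Without them the result can lie anywhere between 0 and 44, so no useful estimate is possible.

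**The case against.** The best defence is that the diary is one source among several. Section II.a introduces it as additional to the medical record, every subject is seen at three visits and called at least monthly, and Visit 3 follows Visit 2 by only 8 weeks. A bleed of any consequence would probably surface. This stands, and it rules out one tempting inference: that bleeding in Lovenox and warfarin subjects goes unrecorded. The documents support only that it has no diary record and that no section prescribes a question to elicit it.

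A second defence is that item 6 gives a coherent reason for the restriction and describes the log as holding drug, dose, date and time, with no mention of reactions. The form also has an open field for the medication, so the injection item may simply be left over from a general-purpose form. That is plausible. But an open medication field also means the form would serve any anticoagulant without redesign, and Section II.a still counts on diaries for adverse reactions.

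A third caution concerns the text available. The body of the Appendix 3 table is not visible, so treating the asterisked list as its side-effect field is an inference. The items listed make it a strong one.

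**Conclusion.** The concern holds in a limited form. Under the stated rule, subjects on Lovenox or warfarin have no diary record of bleeding or injection reactions during the study, and the reason for the rule does not bear on safety. Capture is uneven by drug because of the log, and by arm because the main remaining route, the phone call, is scheduled about four times as often in the Fitbit arm.

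A reader might go further and infer that a chance imbalance in drug mix would produce a false difference in bleeding between the arms. The documents do not support that as a threat to a trial result. Bleeding is not among the outcomes in Section VII or the Statistical Analyses section, no comparison of bleeding between arms is planned, and the log rule is identical in both arms. The feasibility indicators, quality-of-life scores, biomarkers and PTS assessments are untouched.

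The size of the gap cannot be stated, for want of the two shares in Step 4. The conclusion does not depend on them, except that at least some subjects must still be taking Lovenox or warfarin after Visit 1, which the protocol allows. The change is worth making because it is cheap, not because the trial's conclusions are at risk.

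**What to change.** Give the adverse-reaction part of the Appendix 3 log to every subject in both arms for as long as they take any anticoagulant. Keep anti-Xa and INR as the adherence measures for Lovenox and warfarin; those families need not record doses. Amend the Table 1 footnote, item 6, the list of appendices and Appendix 3 so that they agree with Section II.a on which diary supplies adverse reaction data. State that logged bleeding will be summarised descriptively by arm and by drug, with the number of subjects and time on each drug shown beside it.

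The form already exists, so the cost is a text amendment, a small diary burden for Lovenox and warfarin families, and some extra data entry. If that burden is thought too high, one fixed bleeding question at the monthly calls and visits common to both arms would be a lighter alternative. Neither option changes any subject's treatment. Weekly calls may still prompt fuller reporting in the Fitbit arm, and the summary should say so.

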Analyses: The objectives of this trial are to assess the feasibility of the design and to measure the effect size of the intervention. All analyses will therefore be descriptive and will be performed once, at the end of the trial. Means and standard deviations, or when appropriate, medians and semi-inter-quartile ranges will be used to describe demographic and clinical characteristics. Reasons for non-eligibility, lack of consent, dropout and lack of compliance will be documented. For feasibility indicators, we (study investigators and [name]-biostatistician) will describe rate of eligibility (proportion of subjects screened who fully meet trial eligibility criteria to participate in the trial), rate of consent (the proportion of eligible subjects who consent to participate) and rate of loss to follow-up (proportion of randomized subjects who drop out of the trial, in total, and by allocated intervention). We will also describe the level of compliance in the intervention group, calculated as the ratio of who complied with the activity prescription to the number given the prescription. We will consider the trial *successful* if the following criteria are met: rate of eligibility $\geq 30\%$, rate of consent $\geq 30\%$, rate of loss of follow-up $<20\%$, level of compliance $\geq 60\%$ and proportion of subjects who complete the trial $\geq 80\%$. For the clinical outcomes (including the secondary outcomes), we will describe change (means and standard deviations) in the intervention and control groups, from baseline to 6 month, in the QoL scores and PTS biomarkers. Each change score will be interpreted for clinical significance and common responses counted for frequency of occurrence. The impact of the activity

Table 2: Feasibility Indicators

Proportion of screened subjects who meet eligibility criteria: $\geq 30\%$

Proportion of screened subjects who provide consent: $\geq 30\%$

Level of adherence in the intervention arm: $\geq 60\%$

Proportion of subjects who complete the trial: $\geq 80\%$

tracker to promote continued physical activity in the last 2 weeks of the 12-week period would be explored. We will also assess the impact of covariates such as age, sex, BMI, baseline activity, intensity of activity over and above the activity prescription, on change scores.

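### Encouragement and adherence calls run through the four weeks meant to record habitual steps, so the baseline that sets each subject's target is exposed to coaching

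*Combined protocol and SAP*

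**What the plan says.** The schedule for the intervention arm (III. Study Protocol, b. Study Interventions) has three phases. First, subjects "wear the Fitbit for a period of four weeks to establish baseline or 'habitual' activity". From those steps an individual target is derived, "corresponding to a 25% increase above the baseline". Next: "Subjects will be asked to maintain the target steps/day for a period of 8 weeks". In the last four weeks subjects choose whether to keep the higher level or go back to their usual one.

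The rule on calls spans all three phases: "A phone call will be made periodically for encouragement and to ensure adherence to the activity regimen throughout the initial 16-week period". In Table 1 the matching Fitbit-arm row begins "Phone Calls (weekly" and is marked at Visits 1 and 2. No section suspends these calls, or narrows what is said in them, while the baseline is being recorded.

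For the control arm the same section does define call content: "monthly phone contacts will be made to check in with patients/families and remind them about completion of activity logs and follow-up visits".

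The target feeds a primary outcome. Section VII measures adherence as the proportion reaching the weekly step goal in the active eight weeks, and Table 2 sets the success level at 60%. The Analyses text also plans to explore the impact of the "tracker to promote continued physical activity" in the final two weeks of a 12-week period that it does not define.

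**The concern.** A run-in that is meant to capture usual behaviour should not carry contact whose stated purpose is to change that behaviour. In weeks 1-4 there is no target to adhere to, so a coordinator who follows the text has only general encouragement to offer, and weekly calls give about four occasions to offer it.

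Any rise this causes goes straight into the target, because the target is a fixed multiple of the recorded baseline. Two things are at stake. The pilot may be unable to say what increment over usual activity it tested, although its purpose is to inform a definitive trial. And the 60% criterion would be judged against a harder target than the protocol intends.

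A lesser issue concerns continued activity. The Analyses text names the tracker alone, yet calls run alongside it in the weeks concerned.

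**Working it through.** **Inputs.** Phases of 4, 8 and 4 weeks, and a target of 1.25 times recorded baseline (intervention-arm schedule); weekly calls (Table 1); adherence criterion of 60% (Table 2 and Analyses). The documents give no figure for the effect of calls on steps, so the values below are assumptions.

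**Step 1: coverage.** 4 + 8 + 4 = 16, so calls throughout the initial 16 weeks include the whole of the baseline phase.

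**Step 2: effect on the target.** Let H be true habitual steps/day and x the proportion by which calls raise recorded baseline. Recorded baseline = H(1 + x), so target = 1.25 × H(1 + x).

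- x = 0: 1.25, which is the plan's own 25%.
- x = 5%: 1.25 × 1.05 = 1.3125, or 31% above habitual.
- x = 10%: 1.25 × 1.10 = 1.375, or 37.5% above.
- x = 20%: 1.25 × 1.20 = 1.50, or 50% above.

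**Step 3: effect on measured adherence.** Take a subject whose activity in weeks 5-12 is truly 25% above H. The rise measured against recorded baseline is 1.25/(1 + x) − 1.

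- x = 5%: 1.25/1.05 − 1 = 19%.
- x = 10%: 1.25/1.10 − 1 = 14%.
- x = 20%: 1.25/1.20 − 1 = 4%.

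In each case the subject has made the intended increase but is recorded as short of target.

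**Step 4: a call effect that continues.** Calls also run in weeks 5-12. If they raise steps by y in those weeks, on top of a 25% increase from other causes, the measured ratio is 1.25 × (1 + y)/(1 + x). With x = 10% and y = 5% it is 1.25 × 1.05/1.10 = 1.193, compared with 1.136 when y = 0. In the limiting case y = x the ratio returns to 1.25 and the shortfall disappears. The target would still lie above 1.25 × H, as in step 2.

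**Step 5: continued activity.** The 12-week period can be read in two ways. Counted as the 12 weeks after baseline (8 + 4), its last two weeks are weeks 15-16, in the free-choice phase. Counted from first wear, they are weeks 11-12, still under prescription. Calls run in both windows, so neither isolates the tracker.

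**The case against.** The strongest reply is that the text shows an opportunity for coaching and not coaching itself. With no regimen yet in force, early calls may concern only wearing the device, and the wording on frequency is loose. That stands as to size: nothing in the documents shows that steps would rise, or by how much. It does not remove the problem, because the stated purpose of the calls is encouragement and adherence for the whole 16 weeks, and the authors did specify neutral content for controls.

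Several further points stand:

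- Calls are not the only influence on the baseline. An education session on enhanced activity and hands-on tracker training come first, and wearing a tracker may itself change behaviour. Scripting the calls removes one influence of several, though it is a repeated one and easy to remove.
- The proportion meeting the prescribed target can still be calculated, whatever true habitual activity was.
- The calls are openly part of the intervention; the Benefits section says they promote compliance. That is a good defence for weeks 5-12 and a weak one for a baseline phase.
- QoL and biomarkers are assessed at Visit 1, before the weekly calls, and controls wear no Fitbit, so no between-arm comparison of steps is affected.

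A reader might also infer that calls in weeks 13-16 contradict the purpose of that phase and invalidate a test of persistence. The documents do not support this. Keeping the increased activity is one of two permitted choices, so supportive contact does not conflict with it. The protocol does not present those weeks as a test of unassisted persistence. The related analysis is exploratory, has no success criterion, and may not concern those weeks at all.

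**Conclusion.** The concern holds for weeks 1-4. As written, the call rule exposes the baseline to coaching of unknown size, and that baseline sets the target behind a primary feasibility criterion. Under assumed inflations of 5%, 10% and 20%, the nominal 25% becomes 31%, 37.5% and 50% above true habitual activity. Adherence against the 60% level could be understated, by less if the call effect persists into weeks 5-12.

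It would go too far to say that the baseline is contaminated or that the criterion is bound to be biased towards failure. The first is a risk that the documents do not quantify, and the second depends on how far the call effect carries over. For continued activity, what stands is that the window is undefined and that persistence could not be credited to the tracker alone. The plan should be amended, because the protection is nearly free. Sample size and power are not affected.

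**What to change.** Amend the call sentence in the intervention-arm schedule and the weekly-call row of Table 1:

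1. In weeks 1-4, calls cover only device wear, charging, syncing and skin problems. Wear reminders are allowed, since these weeks set the target and completeness of step data enters the withdrawal rule. There is no encouragement to be more active and no feedback on steps.
2. Encouragement and adherence content starts once the target has been set.
3. In the Analyses text, name the exact weeks used to examine continued activity, and describe any persistence as the effect of tracker plus calls. Restricting call content in weeks 13-16 is optional.
4. In the report, note that the education session and tracker wear remain as influences on the baseline.

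Call frequency, staffing and the activity prescription do not change. The cost is a short amendment and a two-version call script, with perhaps slightly less engagement during the run-in.
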